12.5.3. Reporting Standards for Pharmacokinetic

Pharmacokinetic Concentration Data	
PC Windows Non-Linear (WNL) File	
PC WNL file (CSV format) for the non compartmental analysis by Clinical Pharmacology Modelling and Simulation function will be created according to GUI_51487.
 
Note: Concentration values will be imputed as per GUI_51487

Descriptive Summary Statistics, Graphical Displays and Listings	
Refer to IDSL PK Display Standards.
 
Refer to IDSL Statistical Principle 6.06.1.
 
Note: Concentration values will be imputed as per GUI_51487 for descriptive summary statistics/analysis and summarized graphical displays only.

NONMEM/Pop PK File	Not applicable.
Pharmacokinetic Parameter Derivation	
PK parameters to be provided to programmer	The following PK parameters will be derived by CPMS and provided to the programmer: [PK parameters, as defined in Section 9.1.1.2 and Section 9.2.1.2])

Pharmacokinetic Parameter Data	
Is NQ impacted PK Parameters Rule Being Followed	Yes, refer to Standards for Handling NQ Impacted PK Parameters, December 2009.
Descriptive Summary Statistics, Graphical Displays and Listings	Refer to IDSL PK Display Standards.

12.6. Appendix 6: Derived and Transformed Data

12.6.1. General

Multiple Measurements at One Analysis Time Point

 • Mean of the measurements will be calculated and used in any derivation of summary statistics but if listed, all data will be presented. • If there are two values within a time window (as per Section 12.3.1) the value closest to the target day for that window will be used. If values are the same distance from the target, then the mean will be taken. • Participants having both High and Low values for Normal Ranges at any post-baseline visit for safety parameters will be counted in both the High and Low categories of “Any visit post-baseline” row of related summary tables. This will also be applicable to relevant Potential Clinical Importance summary tables.
Study Day

 • Calculated as the number of days from First Dose Date: 
 • Ref Date = Missing → Study Day = Missing • Ref Date < First Dose Date → Study Day = Ref Date – First Dose Date • Ref Date ≥ First Dose Date → Study Day = Ref Date – (First Dose Date) + 1

12.6.2. Study Population

Treatment Compliance

 • Treatment compliance is defined as a participant receiving both doses of study treatment (0 h and 12 h).
Challenge Compliance

 • Challenge compliance is defined as undergoing segmental challenge to the lungs, via bronchoscopy, at 2 hours after the first dose of investigational medicinal product (IMP): 10 mL LPS (4 ng/kg) instilled into the right middle segment and 10 mL saline control instilled into the lingula segment of the contralateral side.

12.6.3. Pharmacodynamic and Biomarker

Derivation of BAL White Blood Cell Counts and Differentials

 • Differential cell count gives the relative percentage of each type of white blood cell and is calculated as follows. $\text{Differential cell type count (\%)} = \frac{\text{Total cell type count (cells/mL)}}{\text{Total white blood cell (leukocyte) count (cells/mL)}}$ 
 • Equivalently, to calculate absolute cell type count:

Derivation of BAL White Blood Cell Counts and Differentials

Total cell type count (cells/mL)

$$= \text{Differential cell type count (\%)} \times \text{total WBC count (cells/mL)}$$

- It is anticipated that pharmacodynamic endpoints and biomarkers will require log-transformation in all analyses to improve model fitting. Following model fitting, back-transformation will occur and treatment effects (GSK2798745 relative to placebo) will be expressed as percentage changes.
- Percentage change, active relative to placebo, will be calculated as:
 Percentage change = $\left(\frac{\text{Active adjusted posterior median}}{\text{Placebo adjusted posterior median}} - 1 \right) \times 100$
- Ratio, active relative to placebo, will be calculated as:
 Ratio = $\frac{\text{Active adjusted median}}{\text{Placebo adjusted median}}$
- Urea concentration data in plasma and BAL will be used to calculate the dilution effect of the lavage which is used to extract the sample from the lung compartment. A correction for dilution will be applied to all BAL analytes to derive corrected concentrations i.e. each BAL analyte will be adjusted to account for the magnitude of dilution during the BAL procedure using urea plasma concentration as a reference point. A dilution factor for each BAL sample will be calculated as BAL urea concentration / plasma urea concentration. Each BAL analyte will be multiplied by this dilution factor to “correct”. Outputs for BAL analytes adjusted for dilution factor may be produced as an exploratory analysis (See [Appendix 11](#): List of Data Displays). Corrected BAL concentrations for dilution factor will be derived as follows:

$$\text{Corrected concentration (pg/ml)} = \text{BAL concentration (pg/ml)} \times \text{Dilution factor}$$

Where,

$$\text{Dilution factor} = \frac{\text{Urea plasma concentration}}{\text{Urea BAL concentration}} \text{ at time (t)}$$

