7.3. Exploratory Pharmacodynamic and Biomarker Analyses

7.3.1. Endpoint / Variables

Table 3 gives the matrices and sampling schemes for each of the exploratory biomarker endpoints.

Table 3 Exploratory Biomarkers and Corresponding Sampling Schemes

Matrix	Endpoint / Analyte	Sampling Scheme
BAL	Albumin SP-D vWF IL-6 IL-8 TNF-alpha MPO Urea White blood cell counts and differentials (except neutrophils)	2h, 26h
Blood	Total protein (plasma) Albumin (plasma) SP-D (serum) vWF (serum) IL-6 (serum) IL-8 (serum) TNF-alpha (serum) Immature SP-B (serum) urea (plasma) CRP (serum)	2h, 3h, 8h, 26h

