2.11.	Evaluable	PD_T2	26h Exploratory BAL Biomarkers (excluding WBCs): Summary of Posterior Distributions and Posterior Probability Statements from the Analyses	Up to 4 pages per analyte. Page 1: Raw baseline values and baseline covariates values predictions are made at. Also add values used to determine predictions for any other covariates included in the model. Page 2: Adjusted posterior medians for each treatment group i.e. model adjusted predictions. 75% and 95% CrI. Page 3: Treatment comparisons in the form of adjusted posterior median absolute differences or percentage changes (dependent on endpoint and transformation). 75% and 95% CrI. Page 4: Posterior probability statements of interest.	SAC [1]
2.12.	Evaluable	PD_T1	Summary of BAL White Blood Cell Types (Totals and Differentials, except neutrophils): by Timepoint (Baseline (2h) and 26h), Lung Lobe (LPS and Saline Challenge) and Treatment Group	One page per analyte. Separate pages for arithmetic and geometric summary statistics.	SAC [1]

Pharmacodynamic: Tables					
No.	Population	IDSL / Example Shell	Title	Programming Notes	Deliverable [Priority]
2.13.	Evaluable	PD_T2	26h BAL White Blood Cell Types (Totals and Differentials, except Neutrophils): Summary of Posterior Distributions and Posterior Probability Statements from the Analyses	
Up to 4 pages per analyte.
 
Page 1: Raw baseline values and baseline covariates values predictions are made at. Also, add values used to determine predictions for any other covariates included in the model.
 
Page 2: Adjusted posterior medians for each treatment group i.e. model adjusted predictions. 75% and 95% CrI.
 
Page 3: Treatment comparisons in the form of adjusted posterior median absolute differences or percentage changes (dependent on endpoint and transformation). 75% and 95% CrI.
 
Page 4: Posterior probability statements of interest.
	SAC [1]
BAL Pharmacodynamic/Biomarker Corrected for Dilution Factor					
2.14.	Evaluable	PD_T1	Summary of All BAL Biomarkers Corrected for Dilution Factor by Timepoint (Baseline (2h) and 26h), Lung Lobe (LPS and Saline Challenge) and Treatment Group	Conditional output. One page per analyte. Separate pages for arithmetic and geometric summary statistics.	SAC [1]
2.15.	Evaluable	PD_T2	All BAL Biomarkers Corrected for Dilution Factor: Summary of Posterior Distributions and Posterior Probability Statements from the Analyses	Conditional output. See programming notes above.	SAC [1]

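### As written, the urea dilution correction in SAP 12.6.3 also multiplies differential cell percentages and urea itself, so the optional corrected BAL outputs would hold meaningless values for both

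*SAP*

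**What the plan says.** SAP 12.6.3 (Pharmacodynamic and Biomarker) sets the scope: "A correction for dilution will be applied to all BAL analytes to derive corrected concentrations". The operation follows: "Each BAL analyte will be multiplied by this dilution factor to" correct it. No analyte is exempted.

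The factor is defined twice in that section. The prose reads "A dilution factor for each BAL sample will be calculated as BAL urea concentration / plasma urea concentration". The displayed equation is the inverse, plasma urea over BAL urea at the same time point.

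The section also states that "Differential cell count gives the relative percentage of each type of white blood cell", calculated as the count of that cell type divided by the total leukocyte count.

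The SAP's lists bring both problem quantities within BAL analytes:

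- Table 3 in SAP 7.3.1 lists urea in the BAL row, followed by "White blood cell counts and differentials (except neutrophils").
- SAP 7.2.1 makes the neutrophil differential a secondary BAL endpoint.

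The corrected displays are equally broad. Table 2.15 is titled "All BAL Biomarkers Corrected for Dilution Factor: Summary of Posterior Distributions and Posterior Probability Statements from the Analyses". Table 2.14 and Figures 2.22-2.25 have the same coverage. SAP 12.6.3 says that such outputs may be produced as exploratory analyses, and the display lists mark these tables and figures as conditional.

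**The concern.** A dilution correction converts an amount per mL of recovered lavage into an amount per mL of the fluid that was sampled. It suits quantities whose measured value falls as more saline is recovered. A percentage of cells does not fall in that way, and urea serves as the yardstick. Multiplying either by the factor produces a number with no biological reading.

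Table 2.15 is to report posterior treatment effects and probability statements. For a differential that was free of dilution, the corrected version would carry the dilution factor into the treatment comparison. An arm difference in lavage dilution could then be read as a drug effect on the cell mix. A corrected BAL urea page would be mislabelled under one definition of the factor and uninterpretable under the other.

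**Working it through.** The plan gives no figure to reproduce here, so the check is algebra on the formulas in SAP 12.6.3.

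**Inputs.** Let P be plasma urea, B BAL urea and D = P/B the lavage dilution. Let N and W be the cell-type and total leukocyte counts per mL in one sample, and x = 100 × N/W the differential in percent. The documents give no urea, dilution or differential values, so D and x below are assumed. Protocol 7.2 describes the 24 h response to this LPS dose as dominated by neutrophils without giving a percentage. I read that as just over half, so x = 51 stands for an LPS-segment sample and x = 2 for a low baseline or saline sample.

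**Dilution cancels in a differential.** Undiluted counts would be N × D and W × D. Their ratio is (N × D)/(W × D) = N/W, so x needs no correction.

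**What the rule does to x.** The displayed equation gives x × D; the prose gives x / D.

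| x | D = 2: equation / prose | D = 10: equation / prose | D = 100: equation / prose | Equation reaches 100% at D = 100/x |
|---|---|---|---|---|
| 2% | 4 / 1 | 20 / 0.2 | 200 / 0.02 | 50 |
| 30% | 60 / 15 | 300 / 3 | 3,000 / 0.3 | 3.33 |
| 51% | 102 / 25.5 | 510 / 5.1 | 5,100 / 0.51 | 1.96 |
| 80% | 160 / 40 | 800 / 8 | 8,000 / 0.8 | 1.25 |

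**What the rule does to urea.**

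- Equation: B × (P/B) = P, which is plasma urea for every D. The LPS and saline samples at 26 h would then show the same value, and Table 3 already lists plasma urea as a blood biomarker at 2, 3, 8 and 26 h.
- Prose: B × (B/P) = B²/P. With an assumed P of 5.0 and D = 10, B = 0.5 and the result is 0.25/5.0 = 0.05, which is neither BAL nor plasma urea.

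**Effect on the comparison.** On the log scale the corrected differential is log x + log D with the equation, or log x − log D with the prose. A factor common to everyone cancels in a treatment ratio. If the geometric mean of D at 26 h differed between arms by a factor g, the ratio before baseline adjustment would shift by g or 1/g. Nothing in the documents gives g or the spread of D.

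**After the fix.** If only N and W are corrected, the differential stays N/W. The values 2, 30, 51 and 80% are unchanged for every D and under either definition.

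**The case against.** Three points deserve weight.

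**The text speaks of concentrations.** The formula is labelled in pg/ml, and a percentage is not a concentration. Listing 34 gives corrected total protein, while the neutrophil listing (Listing 35) has no corrected counterpart. This makes the intended scope less clear, but it is not a limit. Total protein is in µg/mL and is corrected all the same. Urea is a concentration, so this reading would not exempt it. The SAP also excludes white cells by name when it means to (Tables 2.10-2.11, Figures 2.14-2.17), and the corrected displays carry no such exclusion.

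**The outputs are optional.** This stands. A reader might infer that the secondary neutrophil differential is itself contaminated by dilution. The documents do not support that. SAP 7.2.5.1 refers to the default model in 7.1.5.1, neither section calls for correction, and Tables 2.8-2.9 and Figures 2.10-2.13 report the endpoint uncorrected.

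**The striking consequences depend on assumptions.** This also stands. A reader might infer that corrected percentages will always be far above 100% and that corrected urea is always plasma urea. Both follow from the displayed equation only. Under the prose definition percentages shrink. Even under the equation, a 2% differential needs more than 50-fold dilution to pass 100%.

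**Conclusion.** The defect is real but contained. The stated rule covers differential percentages and urea, and the corrected values for both are meaningless whichever definition of the factor is used. That conclusion rests on algebra alone and needs no assumed numbers.

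The reach is limited to the dilution-corrected outputs, if they are produced: Tables 2.14-2.15, Figures 2.22-2.25, and Listing 44 for the exploratory analytes. All are scheduled only for the final reporting effort, so the interim analyses are untouched, as are the uncorrected primary and secondary results.

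The size of the distortion cannot be stated. The percentages above rest on assumed dilutions of 2 to 100 and assumed differentials of 2 to 80%. They show the form of the problem and do not estimate a bias. The point should be settled before the corrected outputs are programmed.

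**What to change.** In SAP 12.6.3:

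- Limit the correction to quantities measured per mL of lavage: total protein, albumin, SP-D, vWF, IL-6, IL-8, TNF-alpha, MPO, absolute cell counts, GSK2798745 and, if assayed, its metabolite GSK3526876.
- State that differential percentages and urea are not corrected.
- Give one definition of the dilution factor, so that prose and equation agree.

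Drop differentials and urea from Tables 2.14-2.15 and Figures 2.22-2.25, and from Listing 44 where they appear. The cost is one or two sentences in the SAP and fewer output pages. No new data are needed, and no planned primary or secondary analysis changes.

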12.11.9. Pharmacokinetic Figures

Pharmacokinetic: Figures					
No.	Population	IDSL / Example Shell	Title	Programming Notes	Deliverable [Priority]
Plasma PK Concentrations					
4.1.	PK	PKCF1P / PK16a	Individual GSK2798745 Plasma Concentration-Time Plot (Linear and Semi-Log)		SAC [1]
4.2.	PK	PKCF2 / PK17	Mean GSK2798745 Plasma Concentration-Time Plot (Linear and Semi-Log)		SAC [1]
4.3.	PK	PKCF3 / PK18	Median GSK2798745 Plasma Concentration-Time Plot (Linear and Semi-Log)		SAC [1]
4.4.	PK	PKCF1P / PK16a	Individual Metabolite GSK3526876 Plasma Concentration-Time Plot (Linear and Semi-Log)	Conditional output.	SAC [1]
4.5.	PK	PKCF2 / PK17	Mean Metabolite GSK3526876 Plasma Concentration-Time Plot (Linear and Semi-Log)	Conditional output.	SAC [1]
4.6.	PK	PKCF3 / PK18	Median Metabolite GSK3526876 Plasma Concentration-Time Plot (Linear and Semi-Log)	Conditional output.	SAC [1]
BAL PK Concentrations					
4.7.	PK	PK_F1	Individual Participant and Median BAL GSK2798745 Concentration-Time Plot	Not urea-corrected BAL concentration. PK_F1 is a loose example. One active treatment group in this study. Use participant-specific attributes map.	SAC [1]
4.8.	PK	PK_F1	Individual Participant and Median BAL GSK2798745 Concentration-Time Plot (Concentration Adjusted for Dilution Factor)	Conditional output. Urea-corrected BAL concentration. PK_F1 is a loose example. One active treatment group in this study. Use participant-specific attributes map.	SAC [1]

Pharmacokinetic: Figures					
No.	Population	IDSL / Example Shell	Title	Programming Notes	Deliverable [Priority]
BAL and Plasma PK Concentrations					
4.9.	Evaluable	PKPD_F1	Scatter Plots of Plasma PK Parameters (C_{MAX} , AUC_{0-26} , C_{26}) v BAL GSK2798745 Concentrations (C_2 , C_{26}).	Only participants on active treatment. Page 1: Plasma C_{MAX} v BAL C_2 . Page 2: Plasma AUC_{0-26} v BAL C_{26} Page 3: Plasma C_{26} v BAL C_{26}	SAC [1]
4.10.	Evaluable	PKPD_F1	Scatter Plots of Plasma PK Parameters (C_{MAX} , AUC_{0-26} , C_{26}) v BAL GSK2798745 Concentrations (C_2 , C_{26}). BAL Concentrations Adjusted for Dilution Factor.	Only participants on active treatment. Page 1: Plasma C_{MAX} v BAL C_2 . Page 2: Plasma AUC_{0-26} v BAL C_{26} Page 3: Plasma C_{26} v BAL C_{26}	SAC [1]

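### SAP 12.6.3 defines the urea dilution factor in two reciprocal ways, and the version in words squares the dilution in the exploratory corrected outputs instead of removing it

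*SAP*

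**What the plan says.** One bullet of SAP 12.6.3 (Appendix 6, derived data) sets out the correction. Its purpose is that "each BAL analyte will be adjusted to account for the magnitude of dilution during the BAL procedure using urea plasma concentration as a reference point".

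The rule is then given twice:

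- **Sentence.** "A dilution factor for each BAL sample will be calculated as BAL urea concentration / plasma urea concentration", followed by "Each BAL analyte will be multiplied by this dilution factor".
- **Equation.** Corrected concentration is BAL concentration times dilution factor, and the factor is displayed as urea in plasma over urea in BAL, at the same time t.

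On status, the bullet first says a correction will apply to every BAL analyte. It then says that outputs using it are exploratory and optional.

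In the list of data displays (SAP 12.11), the corrected outputs are Tables 2.14, 2.15 and 4.4, Figures 2.22 to 2.25, 4.8 and 4.10, and Listings 34, 44 and 56. All are marked conditional except Figure 4.10, the plasma-versus-BAL drug scatter plots, whose title ends "BAL Concentrations Adjusted for Dilution Factor".

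**The concern.** Both versions multiply, and their factors are reciprocals of each other, so a programmer has to choose between opposite rules. Lavage dilutes the sample, so BAL urea lies below plasma urea. The correction must therefore scale the measured value up. The sentence scales it down a second time.

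What is at stake is the set of corrected outputs. Corrected drug concentrations in the lung would be far too low. Corrected protein and biomarker comparisons would carry more dilution noise than the uncorrected ones. Any difference in dilution between arms would be enlarged rather than removed.

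**Working it through.** **Inputs**

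- Both definitions of the factor, and the multiply operation: SAP 12.6.3.
- Urea is itself a listed BAL analyte: SAP 7.3.1, Table 3.
- Log-scale variance of BAL total protein in LPS-challenged lungs, 0.25 (95% CI 0.13 to 0.69), and a minimum observed effect for success of 19% at 30 per arm: Protocol 10.1.
- Dilution D and its spread: assumed, because neither document gives a urea value.

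**1. Algebra.** Let C be the true lung-fluid concentration and D = plasma urea / BAL urea. The measured value is C/D.

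- Equation: (C/D) × D = C.
- Sentence: (C/D) × (1/D) = C/D².

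**2. A check that needs no assumed value.** Apply each rule to urea itself. The equation gives BAL urea × (plasma urea / BAL urea) = plasma urea, which is the reference. The sentence gives (BAL urea)² / plasma urea, which is further from the reference than the raw BAL value whenever the sample is diluted.

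**3. Size of the disagreement.** The two rules differ by a factor of D². Over an assumed range:

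| D | Ratio of the two results |
|---|---|
| 10 | 100 |
| 20 | 400 |
| 50 | 2,500 |
| 200 | 40,000 |

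**4. Log-scale error.** Relative to log C, the error is −log D uncorrected, 0 under the equation and −2 log D under the sentence. Dilution therefore contributes Var(log D), 0 and 4 × Var(log D) respectively.

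**5. Anchoring the variance.** The documents state no dilution figure to reproduce, but the 0.25 can be checked against the protocol's 19%: 1 − exp(−1.645 × 0.5 × √(2/30)) = 1 − exp(−0.2124) = 19.1%. So 0.25 is the working variance of BAL total protein in the sample-size section. No urea correction is mentioned there, so I take it as the uncorrected total, including dilution.

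With SD(log D) = 0.3 (assumed) and D independent of C, dilution contributes 0.3² = 0.09, which is 36% of 0.25:

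- corrected by the equation: 0.25 − 0.09 = 0.16
- uncorrected: 0.25
- under the sentence: 0.16 + 4 × 0.09 = 0.52

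Over a range of assumed dilution shares of the 0.25:

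| Share due to dilution | Equation | Uncorrected | Sentence |
|---|---|---|---|
| 10% | 0.225 | 0.25 | 0.325 |
| 25% | 0.188 | 0.25 | 0.438 |
| 36% (SD 0.3) | 0.16 | 0.25 | 0.52 |
| 50% | 0.125 | 0.25 | 0.625 |

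**6. Imbalance between arms.** Suppose the typical BAL/plasma urea ratio in one arm is 0.8 times that in the other (assumed) and the drug has no effect. The apparent treatment ratio is 0.80 uncorrected, 0.8² = 0.64 under the sentence and 1.00 under the equation. At 0.9 and 0.7 the sentence gives 0.81 and 0.49.

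**The case against.** The best defence is that the bullet nearly resolves itself. The equation is introduced as the derivation to be used, it follows the faulty sentence closely, and it agrees with the stated purpose. Someone who coded the sentence would get corrected values below the measured ones, and quality control would probably catch that. The outputs are exploratory and mostly conditional. Uncorrected BAL drug levels are reported anyway: Table 4.3 and Figure 4.7 are labelled as not urea-corrected. All of this stands, and it lowers the importance of the point. It does not remove the contradiction, because the sentence is a complete, executable rule in current text and Figure 4.10 is not marked conditional.

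Two stronger readings are tempting.

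- **The primary result is at risk.** A reader might infer this because total protein is a BAL analyte and the bullet says the correction applies to all of them. The documents do not support it. The primary model (SAP 7.1), the secondary neutrophil analysis (SAP 7.2) and the interim predictive probabilities (SAP 3.1) state no urea correction, and corrected results form a separate display group.
- **0.25 is the dilution-free variance.** A reader might then add dilution to it, giving 0.25 + 0.09 = 0.34 uncorrected and 0.25 + 4 × 0.09 = 0.61 under the sentence. Protocol 10.1 presents 0.25 as the variance of historical BAL total protein and mentions no urea correction, so the natural sequence is 0.16, 0.25 and 0.52.

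**Conclusion.** The inconsistency is real, and the sentence is the wrong half. It returns C/D² where the equation returns C, which doubles the log-scale dilution error and quadruples its variance. That algebra holds for any D other than 1. It rests on the SAP's own premise that urea tracks dilution. A residual of exactly zero under the equation also needs urea measured without error. The fold differences depend on assumed values of D. The variance figures further assume SD(log D), or a dilution share, and independence of dilution from true concentration.

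The reach is limited to the dilution-corrected exploratory displays. No success criterion, stopping rule or secondary analysis depends on the factor as written. One loose end remains: the PK/PD dataset specification (SAP 12.9.1) has a corrected 26 h total protein variable and does not say whether the correction is for urea or for baseline, so I do not count it as affected. This is a should-fix correction to the text.

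**What to change.** In SAP 12.6.3, change the sentence so that the dilution factor is plasma urea concentration / BAL urea concentration, matching the equation. Leave the multiplication and the equation as they are; they already tie the factor to the time point, and the sentence already ties it to each BAL sample. As a programming check, apply the correction to BAL urea and confirm that it returns plasma urea.

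The cost is one sentence. No data collection, model or display changes. It should be done before any corrected value is derived.
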